**Background:**

Maculopathies such as age-related macular degeneration (AMD) is a prevalent, chronic, and progressive retinal degenerative disease of the macula [1-2]. One of the major clinical consequences of maculopathy is loss of central vision, which impacts daily living activities such as reading, driving and recognizing faces.

Age-related macular degeneration accounts for 8-7% of all blindness worldwide and is the most common cause of blindness in developed countries, especially in people over 60 years of age. Its prevalence is likely to increase as a result of exponential population aging [3 -5]. The global pool prevalence of AMD (based on an age range of 45-85 years) for early, late, and any age-related macular degeneration is 8.01% (95% CI: 3.98-15.49), 0.37% (0.18-0.77), and 8.69% (4.26-17.40), respectively [6].

The projected number of people with age-related macular degeneration was 196 million worldwide in 2020 (95% CI: 140-261) and is expected to increase to 288 million by 2040 [3]. Previous studies have shown that the age-standardized prevalence of early and late AMD in Singapore was 5.1% and 0.5%, respectively [6]. It is interesting to note that there are no major racial differences in the prevalence of AMD in Singapore [6].

In addition, AMD in Singapore is expected to increase over time due to the aging population and longer life expectancy.

This CRYSTALSIGHT system is a proposed home-based precision monitoring telemedicine device that utilizes advanced eye tracking algorithms that enable comprehensive and intelligent assessment of a person's visual performance non-invasively and from the comfort of their home, without the need for manual or expert intervention. CRYSTALSIGHT is an automated method and system for vision assessment of a subject. The method includes the following: determining a set of test patterns for the subject based on a preliminary assessment of an eye of the subject; displaying the set of test patterns sequentially to the subject; collecting data on the subject's gaze in response to each test pattern displayed; and correlating central vision function of the subjects to the collected gaze data.

### **The underlying cause of AMD**

Age-related macular degeneration (AMD) is the most common cause of irreversible blindness in adults  $\geq 60$  years old [7]. The underlying defect appears to be premature dysfunction of the retinal pigment epithelium (RPE), a monolayer responsible for most of the maintenance functions of the neurosensory retina.

The etiology of AMD is multifactorial, with both genetic and other modifiable risk factors contributing to personal risk. The phenotypic risk factors such as drusen and pigment abnormalities become more important to predict disease progression during the course of the disease. Demographic and environmental risk factors such as age and smoking are consistently found to be significantly associated with disease progression, while other risk factors such as sex, body mass index (BMI) and education are less commonly associated [8].

In addition, molecular mechanisms involving the lipid-cholesterol pathway, angiogenic factors, inflammation and immune processes play a critical role in the pathophysiology of disease development and progression [9-10].

## **Disease progression, immediate and late complications of AMD**

AMD can be classified as early, intermediate, or late stage [11]. Minimal visual disturbances may occur in a large proportion of patients with early and intermediate stages of AMD and eventually progress to advanced AMD. The development of these advanced subtypes of geographic atrophy (GA) and neovascular disease (NV) is commonly associated with visual impairment and blindness, which may affect quality of life and lead to loss of independence [12-14].

Progression to Wet AMD (or) neovascular AMD (nAMD) is characterised by the formation of new fragile vessels originating from the choriocapillaris [8]. These new vessels grow into the retina with subsequent leakage and/or hemorrhage that can lead to serous RPE detachment accompanied by a rapid loss of vision and eventually causing a vision-threatening scar in the macula [15]. There are several risk factors that may influence the progression of disease, and the rate at which it progresses may vary among individuals [8].

Imaging techniques that can detect the conversion of an early stage of AMD to late-stage Wet AMD include colour fundus photography (CFP), optical coherence tomography (OCT), fluorescein angiography (FAG), indocyanine green angiography (ICGA), and OCT angiography (OCTA). Whereas CFP, OCT, and FAG can detect exudative nAMD by fluid leakage and haemorrhage [8,16].

## **Treatment of Maculopathies**

Maculopathy is more prevalent with ageing and can result in blurred or distorted vision, often accompanied by a dark patch blocking the center of the visual field. In the management of age-related macular degeneration (AMD), patients are required to attend regular check-ups at the specialist eye clinic by the clinician to monitor if their disease. The eye examinations that patients undergo during these clinic visits which may include fundoscopy and optical coherence tomography. A preventive treatment for exudative or wet AMD is the administration of an intravitreal injection of an anti-vascular endothelial growth factor (anti-VEGF) at these regular clinic sessions.

Although anti-vascular endothelial growth factor (VEGF) injections are an effective treatment for many patients with NV [10, 17], some patients do not respond, there is a large treatment burden, and visual loss continues over time.

There is no treatment for GA. Thus, prevention of advanced disease and finding new and effective treatments remains a significant challenge. Identifying individuals with early and intermediate disease at high risk of progression to advanced stages would lead to earlier intervention and reduced burden of visual loss due to AMD [10].

There are many anti-VEGF treatment strategies aimed at minimizing intravitreal injections without compromising visual outcomes as well as to reduce the need for repeated treatments with the associated cumulative risk of endophthalmitis and other adverse events [18-19].

Currently available anti-VEGF treatment schedules include the “as-needed” (PRN) and the “treat-and-extend” regimens. In an “treat -as-needed” regimen, the patient is examined monthly but not always treated, and treatment can be given only if intraretinal or subretinal fluid is present [19-20]. In a “treat-and-extend” regimen, the patient is always treated, but the intervals between examinations are varied [19-20].

### **Significance of the project and unmet clinical needs**

Although anti-vascular endothelial growth factor (VEGF) injections are an effective treatment for many patients with Wet-AMD [17], there are several unmet needs in treatment of AMD and none of them cures the disease or reverses its course [17, 21 – 23]. Some patients do not respond to VEGF injections. There are no standardized treatment schedules, there is a large treatment burden, and visual loss continues over time. Additionally, the main drawback of anti-VEGF therapy is its high cost, which suppose a significant burden on health systems, and often makes such a regimen unaffordable in clinical practice [24] There is no treatment for GA. Therefore, the prevention of advanced disease like Wet-AMD and finding new and effective treatments remain a significant challenge.

Advances in imaging and genetics and molecular technologies have led to the identification of new risk factors for disease progression, but not all have been evaluated in comprehensive prediction models [8]. Perhaps, comprehensive prediction models could lead to the development of tailored, individualized therapy and improve the personalised healthcare.

The management of AMD is diagnosed and monitored today using clinic-based Optical Coherence Tomography (OCT), however this requires burdensome visits. This CRYSTALSIGHT system is a proposed home-based precision monitoring telemedicine device that utilizes advanced eye tracking algorithms that enable comprehensive and intelligent

assessment of a person's visual performance non-invasively and from the comfort of their home, without the need for manual or expert intervention.

As such, the application of this next-generation OCCUTRACK Technology to develop a comprehensive risk score algorithm and to estimate the risk scores to identify individuals at high risk for disease progression to advanced stages would result in earlier intervention and reduced burden of visual loss due to maculopathy. This approach could enable the tailored individualized Anti-VEGF Therapy to promote personalized medicine and improve the quality of life for these patients.

As such, the application of this next-generation OCCUTRACK Technology to develop a comprehensive risk score algorithm and to estimate the risk scores to identify individuals at high risk for disease progression to advanced stages would result in earlier intervention and reduced burden of visual loss due to AMD. This approach could enable the tailored individualized Anti-VEGF Therapy to promote personalized medicine and improve the quality of life of patients with Wet-AMD.

A Proof-of-Concept (POC) was completed by TTSH clinician ([name]) and AStar-IR scientist to co-develop and patent a software, Automated Vision Assessment and Impairment Detection through Gaze Analysis (AVIGA). AVIGA is now referred to as "CRYSTALSIGHT" as part of the commercialization branding. A local medical incubator, Trendlines Medical Singapore, has licensed it from the research party. This led to the spin-off of a new company- OCCUTRACK Pte Ltd to continue the collaboration with TTSH, focusing on the commercialization of the CRYSTALSIGHT.

AVIGA previously used a costly commercial tobii gaze tracker that could potentially limit consumer adoption, the CRYSTALSIGHT system was designed to mitigate costs by incorporating an AI-augmented video camera with gaze tracking algorithms designed to provide a comprehensive assessment of a patient's vision. With this noninvasive technology, retinal specialists can monitor the real time progression and prognosis of patients with AMD while they are in the comfort of their own home without the need for manual or skilled intervention and expensive equipment.

## 2. STUDY DESIGN

The development of a next-generation 'CRYSTALSIGHT' solution using combinations of a novel and cost-effective eye-tracking system with artificial intelligence-based eye-tracking algorithms that detect macular abnormalities and enable clinicians to review and monitor the prognosis of patients via a web platform through the following deliverables.

- a. Evaluate and improve a home-monitoring regimen involving the self-tests of the CRYSTALSIGHT gaze-tracking system.
- b. To demonstrate that CRYSTALSIGHT has the same or superior gaze-tracking capacities as Tobii.
- c. Evaluate the CRYSTALSIGHT device for its functionality and ease of use as a qualitative measurement tool for patients.
- d. Develop the Design History File (DHF) for regulatory filing requirements.

2. This study will improve on the existing gaze-based scoring methodology for disease activity monitoring over time (delta-change) by quantitatively measuring saccadic speed, pursuit and micro-saccades.

Validation of the machine learning algorithm has been completed with an accuracy of xxx > 85% against gold standard test. The Gold Standard Tests used in this validation of the machine learning algorithm are standard visual acuity (VA) and central visual field (VF) test, which are currently used in standard routine clinical practice.

Using fixation data, the accuracy is 0.91, the sensitivity and specificity are 0.76 and 0.95, respectively. Using smooth pursuit, the accuracy is 0.92, the sensitivity and specificity are 0.82 and 0.95, respectively.

TABLE I  
THE RESULT OF IMPAIRED VISION DETECTION.

	Fixation	Pursuit
accuracy	0.91	0.92
sensitivity	0.76	0.82
specificity	0.95	0.95

The hypothesis of this study is to show that a person's visual performance can be assessed non-invasively and from the comfort of their home, without the need for manual or expert intervention, by utilizing the newly developed 'CRYSTALSIGHT' device. A previous study

utilized a commercial gaze-tracker "Tobii ET5L", the hypothesis of this study establishes that the CRYSTALSIGHT eye tracking device has comparable non-inferior performance to the commercial camera and generates an objective score while minimizing patients' need to interact with the machine. Tobii ET5L is an infrared gaze-tracking camera, whilst CRYSTALSIGHT is a video-based camera. The quantitative outcome of the study may enable the clinical trial team to determine that the CRYSTALSIGHT device performs with acceptable or similar performance metrics to the commercial device, which provides an indicative score for disease activity in patients with maculopathies. The findings of this study could also potentially show that the CRYSTALSIGHT device may be used in a home-based setting to determine macular disease activity over time.

Previous studies have shown the potential of gaze tracking to provide an objective score with relevant diagnostic assistance information while minimizing patients' need to interact with the machine.

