**Study Procedure:**

This cohort study will involve 1 study visit.

**Pre-specified clinical outcome:** The prespecified adverse clinical outcome used in this study will be the **maculopathy** which will be identified by an increase in central retinal thickness (CRT) of at least 100 microns or a loss of best-corrected VA of 5 letters or more.

Clinical Validation will be a cohort study design to evaluate the diagnostic accuracy of the CRYSTALSIGHT device compared to the Tobii gaze-tracker in patients with macular diseases recruited from the medical retina specialty clinic.

This study will be conducted in accordance with the tenets of the Declaration of Helsinki.

The goal is to recruit a minimum number of 20 patients with diagnosed indication of maculopathies who fit the inclusion and exclusion criteria. Adult individuals will be voluntarily recruited from Tan Tock Seng Hospital (TTSH) Ophthalmology SOC clinics after they had been assessed for eligibility based on established clinical diagnosis from the case notes through TTSHs NGEMR. Informed consent for participation in this study will be obtained. Eye gaze tracking test will be automated, and patients will only need to follow through the stimulus/image shown without physical contact with the eye gaze tracker using CRYSTALSIGHT and Tobii. A series of stimulus dots in the form of a pursuit (moving stimulus) or saccade (fixed stimulus and fixed speed) will be presented on the screen and the user under test (UAT) will need to look at the targets presented. The test is similar to Microperimetry and Humphrey's visual field test. A score will be generated at the end of the test.

A research collaboration agreement was established between TAN TOCK SENG HOSPITAL PTE. LTD. and OCCUTRACK MEDICAL SOLUTIONS PTE LTD on the research project titled: CRYSTALSIGHT: "Cohort 1.5" clinical investigation study with OCCUTRACK and Tan Tock

Seng Eye Clinic to further develop remote monitoring of age-related macular degeneration at home using artificial intelligence for eye tracking.

Research Procedures:

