## Sample size calculation

The sample size calculation is based on the intraclass correlation between CRYSTALSIGHT and Tobbi. Our minimum acceptable intraclass correlation coefficient (ICC) is 76% between CRYSTALSIGHT and Tobbi, and the expected ICC is 93%, basing on two- sided significance level of 0.05 and power 0.8, a total of 20 subjects are required. Statistical analysis to assess the eye-tracking performance of CRYSTALSIGHT, will be applied through the following methods:

- The Bland and Altman plot will be used to assess the agreement between CRYSTALSIGHT and Tobbi. The difference between CRYSTALSIGHT and Tobbi of each subject will be plotted on the vertical axis, again, the mean of the two readings of each subject on the horizontal axis. Limits of agreement will be presented in the plot.
- Intraclass correlation Coefficient will be computed using a random effect model, including device type (CRYSTALSIGHT vs. Tobbi) as a fixed factor and subject as a random effect. This model accounts for variability between subjects while assessing agreement between the two devices.

In literature, gaze-tracking accuracy measures such as K-means clustering and Euclidean distances were used and will be evaluated for suitability [35, 36]

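### The protocol aims to show CRYSTALSIGHT non-inferior or superior to Tobii, but its only acceptance value, a minimum ICC of 0.76, tests agreement

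*Protocol*

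**What the plan says.** Protocol, section 2 (Study Design), states the aim in three strengths. Deliverable (b) reads "To demonstrate that CRYSTALSIGHT has the same or superior gaze-tracking capacities as Tobii". The hypothesis is that "the CRYSTALSIGHT eye tracking device has comparable non-inferior performance to the commercial camera". The same paragraph then expects to learn whether the device "performs with acceptable or similar performance metrics to the commercial device".

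Under Study Procedure, the output of the test is described only as follows: "A score will be generated at the end of the test". No direction is given in which one device's score would be the better one.

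Under Sample size calculation, the criterion is "Our minimum acceptable intraclass correlation coefficient (ICC) is 76% between CRYSTALSIGHT and Tobbi, and the expected ICC is 93" per cent, with two-sided significance 0.05, power 0.8 and 20 subjects. Two analyses follow. One is a Bland-Altman plot, for which "Limits of agreement will be presented in the plot". The other is an ICC from a model "including device type (CRYSTALSIGHT vs. Tobbi) as a fixed factor and subject as a random effect", with the comment "This model accounts for variability between subjects while assessing agreement between the two devices". K-means clustering and Euclidean distance are mentioned as accuracy measures whose suitability is still to be judged.

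**The concern.** Non-inferiority and superiority are directional claims. They need a measure on which one device can be better than the other and, for non-inferiority, a margin. The ICC treats the two devices alike, so on its own it cannot say which one performs better.

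Nothing else in the protocol supplies a directional rule:

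- The Bland-Altman limits are displayed without an acceptance limit.
- The fixed device effect has no margin.
- The comparison of diagnostic accuracy with Tobii, mentioned under Study Procedure, has no threshold.
- The Euclidean distance, which could rank the devices against a known target, is not committed to.
- The accuracy figure above 85% in section 2 belongs to a completed algorithm validation against visual acuity and visual field, not to this comparison.

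At stake is the conclusion. The study could be run exactly as planned, meet its criterion, and still not support the two strongest words in its own aim. Section 2 also lists a file for regulatory filing among the deliverables, where that wording would matter.

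**Working it through.** **Inputs.** From Sample size calculation: ICC 0.76 (minimum) and 0.93 (expected), two-sided 0.05, power 0.8, n = 20, two readings per subject. Assumptions of this check: between-subject variance 1, normal errors, and a pass when the lower limit of the two-sided 95% CI of the ICC exceeds 0.76. That pass rule is implied by the sample-size test and is not written out. Pass rates are from 40,000 simulated trials per setting.

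**1. The stated sample size.** For two readings, 1 + 2·ICC/(1 − ICC) is 7.333 at 0.76 and 27.571 at 0.93, a ratio of 0.266. Exact power is P(F > F(0.975; n−1, n−1) × 0.266).
- n = 20: F(0.975; 19, 19) = 2.526, power 0.803.
- n = 19: power 0.780.

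So 20 is right for a two-sided ICC test. The calculation contains no non-inferiority margin.

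**2. Symmetry.** ICC 0.93 with no offset means an error variance per device of 1/0.93 − 1 = 0.0753. Put the whole error variance, 2 × 0.0753 = 0.1505, into one device. The pass rate is about 80 to 81% whether that device is CRYSTALSIGHT or Tobii, for both ICC forms.

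**3. Tobii held fixed.** Swapping the errors also changes the comparator. With Tobii's error variance kept at 0.0753 and no offset, the absolute-agreement pass rates are:

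| CRYSTALSIGHT error variance relative to Tobii's | Pass rate |
|---|---|
| 0 (error-free) | about 99% |
| half | 92% |
| equal | 80% |
| double | 50% |
| triple | 28% |

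The consistency form agrees within about one percentage point. The criterion does respond to CRYSTALSIGHT's precision, but it sets no margin for it relative to Tobii's.

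**4. What the bound implies.** With an offset b and error variances eC and eT, the absolute-agreement ICC is 1/(1 + (eC + eT)/2 + b²/2). A true value above 0.76 requires eC + eT + b² < 2 × (1/0.76 − 1) = 0.632. At the extremes, the offset is below √0.632 = 0.79 between-subject SD, or CRYSTALSIGHT's error variance is below 0.63, about 8 times 0.0753. This is a real limit but a loose one, and it was not chosen as a margin.

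**5. Systematic offset, consistency ICC held at 0.93.**

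| Offset (between-subject SD) | Consistency | Absolute agreement |
|---|---|---|
| 0 | 80% | 80% |
| ±0.1 | 80 to 81% | about 72% |
| ±0.2 | 80 to 81% | about 44% |
| ±0.3 | 80 to 81% | 14% |
| 0.69 | 80% | 0% |

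The last row is where 1/(1 + 0.0753 + b²/2) = 0.76. The rows with ± show sensitivity to bias. Since the score has no stated better direction, they do not show better against worse.

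**6. What n = 20 would support for a directional test.** Paired difference, one-sided 0.025, true difference 0, 80% power: the smallest margin is 0.660 SD of the paired differences. If the reading has consistency ICC 0.93, that SD is √(2 × 0.0753) = 0.388 and the margin is 0.26 between-subject SD. At 0.76 the SD is √(2 × 0.3158) = 0.795 and the margin is 0.52. The protocol gives no SD for a Euclidean-distance metric.

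**The case against.** The best defence is that the protocol is really about agreement. Deliverable (b) offers equality or superiority as alternatives, so showing sameness meets it. The hypothesis couples non-inferior with comparable and then falls back on similar performance. No superiority test is planned. Agreement also bounds inferiority, as step 4 shows. The ICC form, Bland-Altman limits and choice of accuracy metric may be fixed in an analysis plan that is not at hand.

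Much of this stands. The agreement analysis suits an agreement aim, n = 20 is correct for it, and details left to an analysis plan are not counted here as omissions. What does not fall away is that the protocol itself fixes the aim, the hypothesis, the acceptance value and the sample size, and the directional words in the first two have no counterpart in the last two. A margin added later would not have informed n = 20.

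A reader might infer from the symmetry that a better CRYSTALSIGHT fails as often as an equally worse one. That is not so in general: with Tobii fixed and no offset, a more precise CRYSTALSIGHT passes more often (step 3). The equal pass rates for positive and negative offsets concern bias, which an agreement test should penalise.

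**Conclusion.** The point holds as a mismatch between claim and criterion. Meeting an ICC minimum of 0.76 supports words such as same, comparable or similar, which the protocol also uses. It does not test non-inferiority against a margin and cannot show superiority.

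The symmetry of the ICC needs no assumption. The pass rates rest on normal errors, between-subject variance 1, the inferred pass rule and, for step 3, an assumed Tobii error variance of 0.0753. The offsets are illustrative. The contrast of 80% against 0% at 0.69 SD arises only if the consistency form is used. The fixed device factor permits that form, but the stated purpose of assessing agreement points the other way.

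Two stronger readings are not supported. The sample size is not wrong, and the plan is not useless for its aim, because its agreement part is sound. The point should be fixed, and mostly by rewording.

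**What to change.** Preferred: in section 2, replace the non-inferior and same-or-superior wording with an agreement claim, for example: *Agreement between CRYSTALSIGHT and Tobii is concluded if the lower limit of the two-sided 95% CI of the two-way, single-measurement, absolute-agreement ICC exceeds 0.76. The Bland-Altman mean difference (CRYSTALSIGHT minus Tobii) with its 95% CI and the limits of agreement are reported alongside.*

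This needs no new data or patients. It gives up the directional words, and its power depends on what 0.93 meant. If 0.93 was a consistency ICC, power is about 80%, 72% and 44% at offsets of 0, 0.1 and 0.2 between-subject SD. If it was already an absolute-agreement ICC, power is about 80%, 75% and 51%. At ICC 0.93 with no offset, the CI of the mean difference would extend about 2.093/√20 × 0.388 = 0.18 between-subject SD either side.

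Keep the directional claim only if one target-referenced accuracy metric and a margin for the paired difference are fixed before data collection, provided both devices record the same task. Non-inferiority would then require the 95% limit on the unfavourable side to lie within the margin, and superiority the whole interval on the favourable side of 0. What n = 20 can support would have to be restated, using an SD that the protocol does not give.
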